### 7.1.1. Multicenter Studies

Study participants will be recruited from 7 study sites.

Following database lock, if potentially impactful site-to-site variation is noted, basic descriptive analyses of baseline demographics, medical history, or other key points will be repeated for each site individually in order to allow qualitative exploration of site-to-site variability.

### 7.1.2. Assessment Time Windows

Allowable visit windows are detailed in Section 10.6 of the protocol.

Unscheduled visits may also occur throughout the study if creatinine increases or other concerns arise between regularly scheduled visits.

Generally, all data will be included in analyses, regardless of time of assessment.

### 7.1.3. Timing of Analyses

All analyses will be conducted following database lock.

### 7.1.4. Multiple Comparisons/Multiplicity

The analysis is primarily descriptive and will not be adjusted for multiple comparisons.

## 8. ENDPOINT EVALUATION

### 8.1. Primary Endpoint

The primary efficacy endpoint will be the change in inflammation as measured by the percentage area of cortex occupied by inflammatory cells using computer-assisted quantitative image analysis on the biopsy 7 months after study group allocation, expressed as the percent change relative to the baseline biopsy. The subject in the darTregs group will be excluded from efficacy analyses.

The safety of polyTregs (Group 2) and darTregs (Group 3) will be described in comparison with CNI-based maintenance IS therapy (Group 1) by:

1. The timing and incidence of Banff 2A or higher acute cell-mediated rejection and/or acute antibody mediated rejection.
2. The timing and incidence of study defined Grade 3 or higher infection.

#### 8.1.1. Computation of the Primary Endpoint

- Primary Efficacy Endpoint
  - Percent change in inflammation at 7 months after group allocation relative to baseline biopsy.
- Primary Safety Endpoint
  - The timing and incidence of Banff IIA or higher acute cell-mediated rejection and/or acute antibody mediated rejection.
    - **Severe Acute Cell-Mediated Rejection-** Acute cell-mediated rejection was defined using the Banff 2007 criteria. Participants with a Banff grade of greater than or equal to IIA were determined to have met the endpoint. Severity is graded as IA, IB, IIA, IIB, or III, with IA being the mildest form of cellular rejection and III being the most severe form of cellular rejection.
    - **Acute Antibody Mediated Rejection-** Antibody mediated rejection was defined as diffusely positive staining for C4d, presence of circulating anti-donor antibodies, and morphologic evidence of acute tissue injury.
  - The timing and incidence of study defined Grade 3 or higher infection.
    - Severe infection was defined in the study as a Grade 3 or higher infection that was culture-proven and clinically diagnosed. Severity is graded as 1 through 5, with 1 being least severe to 5 being most severe. Grade 3 is any infection associated with hemodynamic compromise requiring pressors; any infection necessitating ICU level of care; any infection necessitating operative intervention; any infection involving the central nervous system; any infection with a positive fungal blood culture; any proven or probable aspergillus infection; any tissue invasive fungal infection; any

pneumocystis jiroveci infection. Grade 4 is any life-threatening infection. Grade 5 is any infection resulting in death.

### **8.1.2. Primary Analysis of the Primary Endpoint**

The ANOVA method or Kruskal-Wallis test (or t-test for comparison of Groups 1 and 2) will be used to compare treatment groups on the mean or median percent change in inflammation at 7 months post-group allocation, relative to baseline biopsy. This method will be run on the mITT1 population, subset to participants that have available LCA data from the 7 month visit post-group allocation.

The Fisher's Exact or Cochran-Mantel-Haenszel tests will be used to compare the treatment groups on the incidence of severe acute cell-mediated rejection and/or acute antibody mediated rejection. This method will be run on the mITT1 population, subset to participants that have available Banff data.

The ANOVA method or Kruskal-Wallis test (or t-test for comparison of Groups 1 and 2) will be used to compare treatment groups on the mean or median time of event of severe acute cell-mediated rejection and/or acute antibody mediated rejection. This method will be run on the mITT1 population, subset to participants that have available Banff data.

The Fisher's Exact or Cochran-Mantel-Haenszel tests method will be used to compare the treatment groups on the incidence of severe infection. This method will be run on the mITT1 population.

The ANOVA method or Kruskal-Wallis test (or t-test for comparison of Groups 1 and 2) will be used to compare treatment groups on the mean or median time of event of severe infection. This method will be run on the mITT1 population.

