15. Statistical Considerations and Analytical Plan	70
15.1. Overview	70
15.2. Measures to Minimize Bias	70
15.3. Analysis Plan.....	70
15.3.1. Analysis Samples	70
15.3.2. Endpoint Assessments	70
15.3.3. Descriptive Analyses	73
15.4. Interim Analyses.....	74
15.5. Sample Size Considerations	74
16. Identification and Access to Source Data	76
16.1. Source Data	76
16.2. Access to Source Data	76
17. Protocol Deviations	77
17.1. Protocol Deviation Definitions	77
17.2. Reporting and Managing Protocol Deviations	77
18. Ethical Considerations and Compliance with Good Clinical Practice.....	78

18.1.	Statement of Compliance	78
18.2.	Informed Consent Process	78
18.3.	Privacy and Confidentiality	78
19.	Publication Policy	79
20.	References	80
	Appendix 1. Donor Assessments	86
	Appendix 2. Group 1 Recipient Schedule of Events	87
	Appendix 3. Group 2 Recipient Schedule of Events	88
	Appendix 4. Manufacturing Timeline	89

Glossary of Abbreviations

CFR	Code of Federal Regulations
COVID-19	Coronavirus Disease 2019
CRF	Case Report Form
CRM	Common Response Module
CTCAE	Common Terminology Criteria for Adverse Events
DAIT	Division of Allergy, Immunology, and Transplantation
darTregs	Donor Alloantigen Reactive T Regulatory Cells
DSMB	Data Safety Monitoring Board
FDA	Food and Drug Administration
GCP	Good Clinical Practice
ICH	International Conference on Harmonization
IND	Investigational New Drug
IRB	Institutional Review Board
kSORT	Kidney Solid Organ Response Test
mTOR	Mammalian Target of Rapamycin
NIAID	National Institute of Allergy and Infectious Diseases
PI	Principal Investigator
polyTregs	Polyclonal T Regulatory Cells
Mycophenolate REMS	Mycophenolate Risk Evaluation and Mitigation Strategy
SAE	Serious Adverse Event
SAP	Statistical Analysis Plan
SAR	Suspected Adverse Reaction
SARS-CoV2	Severe Acute Respiratory Syndrome Coronavirus 2
SCI	Subclinical Inflammation
SOP	Standard Operating Procedure
SUSAR	Serious Unexpected Suspected Adverse Reaction

Study Definitions Page

Acute Cell-mediated Rejection	Banff 2007 Type 1A or higher and clinical treatment for acute rejection. Central reading will be utilized when accounting for study stopping rule and for safety endpoint.
Severe Acute Cell-mediated Rejection	Banff 2007 Type 2A or higher and clinical treatment for acute rejection. Central reading will be utilized when accounting for study stopping rule and for safety endpoint.

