8.3. Kidney Biopsy

Study participants will undergo surveillance biopsies as standard of care between 3 and 7 months after transplantation and approximately one year after transplantation. Research specimens will be collected during these procedures and digital images will be sent to the central pathologist for scoring. The biopsy obtained 3-7 months after transplantation will be used to determine study eligibility and local read will be confirmed by central pathologist. The one-year biopsy will fall 7 months after study group assignment and will be used to assess the efficacy endpoint. The one-year biopsy and all for-cause biopsies will be reviewed by the central pathologist.

Additionally, a protocol kidney biopsy will be performed 2 weeks after polyTreg infusion (Group 2). This biopsy is for research purposes only and will be used for mechanistic assays and to confirm eligibility for mTOR conversion. This biopsy will be reviewed by the central pathologist.

9. Known and Potential Risks and Benefits to Participants

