### 3. PROTOCOL SUMMARY

Title	Treg Adoptive Therapy in Subclinical Inflammation in Kidney Transplantation
Short Title	Tregs Infusion for Inflammation Suppression
Clinical Phase	I/II
Number of Sites	7
IND Sponsor/Number	NIH/NIAID/DAIT/ #16626
Study Objectives	

1. To assess the safety of polyTregs infusions and the safety of converting from CNI-based maintenance therapy to mTOR inhibitors after Treg therapy in adult kidney transplant recipients (see Study Definitions page).

2. To assess the efficacy of polyTregs infusions in reducing inflammation in adult kidney transplant recipients (see Study Definitions Page).

Study Design	
This is a multi-center, open-label, randomized, controlled safety and efficacy trial with 2 cohorts, maintenance CNI-based immunosuppression therapy and polyTregs infusion, to achieve inflammation suppression in adult kidney transplant recipients. Eligible participants will either continue maintenance CNI-based immunosuppression therapy or will receive a single infusion of polyTregs (<math>550 \pm 450 \times 10^6</math>). All participants will undergo biopsies to determine study eligibility and at 7 months after study group allocation. Participants who received a polyTregs infusion will undergo an additional biopsy 14 days after polyTregs infusion.
 
The original study design included a third treatment arm of donor alloantigen reactive Tregs (darTregs). One participant was treated with darTregs prior to protocol version 9.0 in which this treatment arm was eliminated due to excessive manufacturing failures.

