**Population-level summary:**

- **polyTreg infusion reactions - mITT2**
- **Acute rejection using Banff grading** – mITT1, subset to participants that have available Banff lab data
- **Acute rejection after converting to mTOR therapy after polyTregs infusion** - mITT2
- **Proportion of participants exhibiting  $\geq 25\%$  decrease of inflammation between baseline kidney biopsy and the week 2 kidney biopsy** – mITT1, subset to participants with available LCA data from week 2 visit
- **Proportion of participants exhibiting  $\geq 50\%$  decrease of inflammation between baseline kidney biopsy and the week 2 kidney biopsy** – mITT1, subset to participants with available LCA data from week 2 visit
- **Proportion of participants exhibiting  $\geq 25\%$  decrease of inflammation between baseline kidney biopsy and the month 6 kidney biopsy** – mITT1, subset to participants with available LCA data from 6 month visit
- All other endpoints will use the mITT1 sample

**Variable:** Secondary timing endpoints including:

Endpoint	Time Frame
polyTreg infusion reactions	405 days post-group allocation
Culture-proven and clinically diagnosed infections	405 days post-group allocation
Acute rejection using Banff grading	405 days post-group allocation
BK viremia after polyTregs infusion	405 days post-group allocation
CMV reactivation after polyTregs infusion	405 days post-group allocation
>10% decrease in eGFR compared to baseline	405 days post-group allocation
Acute rejection after converting to mTOR therapy after polyTregs infusion	69 days post-group allocation to 405 days post-group allocation

**Analysis:** For each of the above timing endpoints, the mean or median time of event (study days since start of treatment) will be reported by treatment group and compared using ANOVA or the Kruskal-Wallis test (or t-test for comparison of Groups 1 and 2).

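### The SAP drops the treatment condition from severe cell-mediated rejection without listing the change, and only Group 2 has a week-2 biopsy on which an untreated finding could then count

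*SAP*

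**What the plan says.** **Definition.** The protocol's Study Definitions page defines severe acute cell-mediated rejection as "Banff 2007 Type 2A or higher and clinical treatment for acute rejection", and acute cell-mediated rejection as "Banff 2007 Type 1A or higher and clinical treatment for acute rejection". Both use central reading for the safety endpoint. The same page limits treatment of rejection to IV steroids and/or Thymoglobulin. SAP 8.1.1 says instead: "Participants with a Banff grade of greater than or equal to IIA were determined to have met the endpoint". It mentions neither treatment nor central reading. Antibody mediated rejection has the same definition in both documents, with no treatment condition in either. For the secondary all-grade endpoint, SAP 8.2.1 refers to Banff grading and is silent on treatment.

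**Biopsies.** Both arms have the eligibility biopsy and one at 7 months after allocation. SAP Section 3 adds: "Participants who received a polyTregs infusion will undergo an additional biopsy 14 days after polyTregs infusion". Protocol 8.3 says of that biopsy: "This biopsy is for research purposes only and will be used for mechanistic assays and to confirm eligibility for mTOR conversion". It is read centrally.

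**Population.** Protocol Table 7 uses mITT1 for the rejection endpoints. SAP 8.1.2 narrows this: "This method will be run on the mITT1 population, subset to participants that have available Banff data". SAP 8.2.1 does the same for all-grade rejection: "mITT1, subset to participants that have available Banff lab data".

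**Changes and sensitivity.** SAP Section 10 discloses the narrower population but not the changed definition. SAP 8.1.3 plans no sensitivity analysis.

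**The concern.** The treatment condition keeps an untreated lesion on a research biopsy from counting as a rejection event. Without it, the extra Group 2 biopsy can generate events that Group 1 has no scheduled opportunity to generate. Nothing in either document separates week-2 findings from the between-arm comparison.

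Timing is affected too, because SAP 8.1.2 compares time of event between arms. A lesion present at Visit 2 can be dated then in Group 2. In Group 1 it would surface only through a for-cause biopsy or at Visit 5.

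At stake is the reading of the primary safety result. With 7 per arm, readers will look at raw counts, and one or two events found by an extra look would change the picture.

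**Working it through.** The documents give no event rate, power or sample size for the rejection endpoints (protocol 15.5 says none was calculated), so there is no stated figure to reproduce. The check compares the texts and then illustrates the size.

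**Step 1. Definitions side by side.**

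| Component | Protocol | SAP | Listed in SAP Section 10? |
|---|---|---|---|
| Severe cell-mediated rejection | 2A or higher and treatment | IIA or higher | No |
| All-grade cell-mediated rejection | 1A or higher and treatment | Silent on treatment | No |
| Antibody mediated rejection | No treatment condition | Same | No change |

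**Step 2. Scheduled post-allocation biopsies.** Group 1 has one (month 7). Group 2 has two (week 2 and month 7).

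**Step 3. Size, illustration only.** Let q be the yield per scheduled look and f the probability of detection by a for-cause biopsy, equal in both arms, with independent looks and no true difference.

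- Group 1: 1 − (1 − f)(1 − q)
- Group 2: 1 − (1 − f)(1 − q)²

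The only yield in the documents is protocol Table 1: 31/380 = 8.2%, any-grade rejection on 6-month surveillance biopsies at one site. The values of f are assumptions.

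| q | f | Group 1 | Group 2 | Ratio |
|---|---|---|---|---|
| 2% | 0 | 2.0% | 4.0% | 1.98 |
| 5% | 0 | 5.0% | 9.8% | 1.95 |
| 8.2% | 0 | 8.2% | 15.7% | 1.92 |
| 20% | 0 | 20.0% | 36.0% | 1.80 |
| 8.2% | 5% | 12.8% | 19.9% | 1.56 |
| 8.2% | 10% | 17.3% | 24.1% | 1.39 |

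With f = 0 the ratio is 2 − q, so a value near 2 is built into the assumptions. Correlated looks lower it further.

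At q = 8.2% and f = 0, expected events among 7 are 0.57 in Group 1 and 1.10 in Group 2. Group 2 shows more events than Group 1 with probability 0.50 and fewer with probability 0.18.

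**Step 4. Timing.** Visits 2 and 5 are 182 − 14 = 168 days apart in Group 2, and 223 − 55 = 168 days apart in Group 1. That is the scheduled gap by which the same lesion could be dated differently.

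**Step 5. Denominator.** Inclusion criterion 4 requires a Banff-scored eligibility biopsy. If baseline data count, the subset removes nobody. If post-baseline data are required, a Group 2 participant qualifies on week 2 alone, while a Group 1 participant needs the month-7 or a for-cause biopsy, so Group 1 loses people more readily. One event then reads 1/7 = 14.3%, 1/6 = 16.7% or 1/5 = 20.0%, depending on who remains.

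**Step 6. Testing.** Fisher's exact test at 7 against 7 gives p = 0.070 for 0 against 4 events and p = 0.021 for 0 against 5. A detection artefact of the size in Step 3 is unlikely to produce a nominally significant test.

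**The case against.** The strongest reply is that the endpoint is descriptive and unpowered, that week 2 is a labelled visit, and that event timing is reported. With 14 participants, anyone reading the listings could pick out a week-2 event. This stands as an argument about severity. It also means a reader should not infer that a real excess of rejection could never be told apart from the extra look. It does not reconcile the definitions, and no planned table makes the separation.

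A second reply is that the treatment condition has a cost. The core pathologist is blinded (protocol 15.2) and the sites are not, so requiring treatment brings an unblinded decision into the endpoint. That is a fair reason to debate the definition. It is not a reason for the SAP to differ from the protocol without saying so.

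Third, a reader might infer that the Banff-data subset adds to the bias against polyTregs. The documents do not support this. Under one reading the subset has no effect. Under the other it tends to shrink the Group 1 denominator, which raises Group 1 incidence and partly offsets the extra look. Nor is a participant without post-baseline data simply someone who never needed a biopsy: both arms have a scheduled month-7 biopsy, so that person's centrally read status is unknown.

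Finally, simply removing week-2 findings from the comparison would be a poor remedy. A treated early rejection could then vanish from the primary safety contrast, although the stopping rule in protocol 13.3 counts severe or antibody mediated rejection within 6 weeks of infusion. This objection stands and shapes the fix.

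**Conclusion.** The concern holds in limited form. The SAP changes the definition of a primary safety component, severe acute cell-mediated rejection, and does not list the change. Combined with the Group 2-only biopsy, this lets untreated week-2 findings enter the comparison and tilts incidence and timing against polyTregs. The direction follows from the design. The size is not known for 2A or higher and may be much smaller than illustrated. The illustration is closer to the secondary all-grade endpoint, and transfer is uncertain even there, because participants are selected on a biopsy without v > 0, [ptc + g] ≥ 2 or C4d above the stated limits.

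Two stronger readings are not supported. The ratio of 1.9 is not an estimate for the primary endpoint: it assumes independent looks, equal yield per look and no for-cause detection. And antibody mediated rejection has lost no treatment condition, because neither document gives it one.

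The denominator rule is a separate ambiguity. Severity is should-fix: the harm is a distorted descriptive contrast with 7 per arm, not a false significant test.

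**What to change.** - **SAP 8.1.1, and 8.2.1 for all-grade rejection:** use the protocol definition for cell-mediated rejection (Banff grade plus clinical treatment, central reading). Leave antibody mediated rejection as it is. If dropping the treatment condition was deliberate, list it in Section 10 with the reason and align the protocol.
- **SAP 8.1.2:** keep all events, including those at week 2, in the primary safety comparison. Add the same comparison without events found only on the week-2 protocol biopsy, for incidence and timing. Tabulate week-2 findings for Group 2. This is needed even with the protocol definition restored, because a treated week-2 finding still has no matching look in Group 1.
- **SAP 8.1.2 and 8.2.1:** return to the full mITT1 denominator for the rejection endpoints, and show by arm how many participants have no post-baseline biopsy.

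The cost is SAP wording and one extra table. No visit, procedure or treatment changes, and no data are lost.

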### **8.1.3. Sensitivity Analyses of the Primary Analysis**

No sensitivity analysis is planned.

### **8.1.4. Secondary Analyses of the Primary Endpoint**

No secondary analysis of the primary endpoint is planned.

## **8.2. Secondary Endpoints**

All secondary endpoint analyses will use the mITT1 population, unless otherwise specified.

### **8.2.1. Endpoints**

**Variable:** Secondary incidence endpoints including:

Endpoint	Time Frame
polyTreg infusion reactions	405 days post-group allocation
Culture-proven and clinically diagnosed infections	405 days post-group allocation

Acute rejection using Banff grading	405 days post-group allocation
BK viremia after polyTregs infusion	405 days post-group allocation
CMV reactivation after polyTregs infusion	405 days post-group allocation
>10% decrease in eGFR compared to baseline	405 days post-group allocation
Acute rejection after converting to mTOR therapy after polyTregs infusion	69 days post-group allocation to 405 days post-group allocation
Proportion of participants exhibiting $\geq 25\%$ decrease of inflammation between baseline kidney biopsy and the week 2 kidney biopsy	Baseline biopsy to Week 2 kidney biopsy
Proportion of participants exhibiting $\geq 50\%$ decrease of inflammation between baseline kidney biopsy and the week 2 kidney biopsy	Baseline biopsy to Week 2 kidney biopsy
Proportion of participants exhibiting $\geq 25\%$ decrease of inflammation between baseline kidney biopsy and the month 6 kidney biopsy	Baseline biopsy to 6 month kidney biopsy (for polyTregs infusion group). Baseline biopsy to 7 months post-group allocation (for maintenance therapy group).

**Analysis:** For each of the above incidence endpoints, the proportion of participants with events will be reported by treatment group and compared using Fisher's Exact test or a Cochran-Mantel-Haenszel test.

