3.3. Secondary Safety Endpoints

3.3.1. Secondary Safety Endpoints

The safety of PolyTregs (Group 2) will be described in comparison with CNI-based maintenance IS therapy (Group 1) by:

1. Timing, incidence, and severity of polyTregs infusion reaction
2. Timing, incidence, and severity of culture-proven and clinically diagnosed infection after PolyTreg infusion
3. Timing, incidence, and severity of acute rejection using Banff grading
4. Timing and incidence of BK viremia and CMV reactivation
5. Timing and incidence of > 10% decrease in eGFR compared to baseline

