10.3.2. Treg Infusion Visit

Eligibility for Treg infusion will be reviewed at the time of the study visit. When applicable, a urine pregnancy test must be confirmed negative prior to infusion. Blood will be drawn for local laboratory tests. Subjects will receive the polyTreg infusion no later than 62 days after central biopsy confirmation. The Treg infusion visit requires an overnight stay in the hospital or research unit for observation.

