10.6. Visit Windows

Study visits should take place within the time limits specified below (Table 2). The designated visit windows for each scheduled visit are also indicated on the Schedules of Events.

Table 2. Visit Windows	
Study Visit	Visit Window
Study Eligibility Biopsy	5 months \pm 8 weeks
Study Eligibility/ Study Group Allocation	\leq 2 weeks after qualifying biopsy
Group 1 Only	
Day 41/ Visit T0-G1	\pm 3 days
Day 48/ Visit 1	\pm 5 days
Day 55/ Visit 2	
Day 69/ Visit 3	
Day 125/ Visit 4	
Day 223/ Visit 5	\pm 14 days
Day 405/ Visit 6	
Group 2	
PBMC Collection Visit T-16	Dictated by infusion date and manufacturing timeline.
Treg Infusion Day / Visit T0	Infusion can occur any time up to and including day 62 after central pathology confirmation.
Visit T1 / Day 1	\pm 1 hour (Group 2)
Visit 1 / Day 7	\pm 1 day
Visit 2 / Day 14	\pm 3 days
Visit 3 / Day 28	
Visit 4 / Day 84	
Visit 5 / Day 182	\pm 14 days
Visit 6 / Day 364	\pm 14 days

11. Mechanistic Assays

The goal of the mechanistic studies in this trial is to evaluate the impact of polyTregs on the immunological profiles of kidney transplant recipients. We will accomplish this by determining: 1) impact of Treg infusion on the numbers of circulating and graft-infiltrating Tregs; 2) impact of Treg infusion on the inflammation in the graft; 3) impact of Treg infusion on the peripheral blood biomarkers of rejection and graft injury.

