Appendix 4. Manufacturing Timeline

Central Biopsy Reading	Randomization to occur as soon as eligibility is confirmed, no later than 14 days after central biopsy confirmation.		Group 2 Recipient Draw*	Group 2 PolyTreg Infusion																																																											
Randomization Day	##	##	34	48																																																											
Post Biopsy Day	0	1	2	3	4	5	6	7	8	9	10	11	12	13	14	15	16	17	18	19	20	21	22	23	24	25	26	27	28	29	30	31	32	33	34	35	36	37	38	39	40	41	42	43	44	45	46	47	48	49	50	51	52	53	54	55	56	57	58	59	60	61	62

*Group 2 recipient draw must occur 16 days (14-16 days for UCSF) prior to infusion date.

Amendment 8: Group 1 SOE will maintain Day 0 as day of study group assignment. Day 0 label was removed from the Group 2 and 3 SOE to avoid confusion. For Group 2 and 3, the day of infusion will no longer be linked to study group assignment but rather to central biopsy reading confirmation.

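### SAP 8.2.1 counts secondary safety events over a fixed 405 days from allocation, a frame that fits Group 2 only if infusion falls on allocation day 41

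*SAP*

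**What the plan says.** **Time frames.** SAP 8.2.1 gives six secondary safety rows the frame "405 days post-group allocation": infusion reactions, infections, acute rejection, BK viremia, CMV reactivation and a fall of more than 10% in eGFR. Rejection after mTOR conversion runs from "69 days post-group allocation to 405 days post-group allocation". The timing table repeats these frames but measures time to event in study days from the start of treatment.

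**Where counting starts.** Protocol 3.3.1 words the infection endpoint as "Timing, incidence, and severity of culture-proven and clinically diagnosed infection after PolyTreg infusion", and the SAP synopsis (section 3) agrees. The infection row in SAP 8.2.1 has no such restriction, and neither does the matching row in protocol Table 7. The BK row reads "BK viremia after polyTregs infusion", and the CMV row is restricted in the same way. Both use mITT1, which includes Group 1.

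**Calendars.** Group 1 visits are counted from allocation, from "Day 41/ Visit T0-G1" to "Day 405/ Visit 6" (protocol 10.6). Group 2 visits are counted from infusion, the last at day 364 (protocol 10.4). On the infusion date, protocol 10.3.2 says: "Subjects will receive the polyTreg infusion no later than 62 days after central biopsy confirmation". The note to Appendix 4 adds that "the day of infusion will no longer be linked to study group assignment but rather to central biopsy reading confirmation".

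**General rule.** SAP 7.1.2 says that, in general, all data are used whatever the time of assessment.

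**The concern.** The visit schedule makes the arms parallel from a common T0, which is infusion in Group 2 and the day-41 visit in Group 1. The secondary safety frames do not use it. They apply Group 1's allocation-based calendar to an arm whose follow-up starts at a variable infusion date.

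Three things follow if the text is applied literally. Group 2 events that precede any polyTreg exposure can count as polyTreg-arm events, including infections outside the endpoint as protocol 3.3.1 defines it. BK and CMV are compared between arms with a start that exists in only one of them. A Group 2 participant infused late can have the final visit fall outside the frame. That visit matters for BK: in the Group 1 schedule (Appendix 2), BKV PCR after screening is planned only at days 223 and 405, apart from clinically indicated biopsies, and Group 2 appears to follow the same pattern.

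Two analysts working from this SAP could obtain different counts. SAP 8.2.1 compares those counts with Fisher's exact or Cochran-Mantel-Haenszel tests, with 7 participants planned per arm.

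**Working it through.** **1. Where 405 comes from.** Group 1 visit day minus the matching Group 2 post-infusion day (protocol 10.4 and 10.6):

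48 − 7 = 55 − 14 = 69 − 28 = 125 − 84 = 223 − 182 = 405 − 364 = 41.

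So 405 = 41 + 364, and the mTOR start is 69 = 41 + 28. Both figures assume infusion on allocation day 41.

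**2. Range of the infusion day, T (days from allocation).**
- Earliest: blood is drawn 16 days before infusion (14–16 at UCSF, Appendix 4). A draw on the allocation day gives T of about 14–16.
- Latest: infusion may occur up to day 62 after central confirmation. Allocation on the confirmation day gives T = 62. Allocation at the 14-day limit gives T = 62 − 14 = 48.

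**3. Effect of T on a 405-day frame.** Pre-infusion days = T. Post-infusion days in the frame = 405 − T. Nominal Visit 6 = T + 364. Days past the frame = max(0, T − 41).

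| T | Pre-infusion days (share of 405) | Post-infusion days in frame | Nominal Visit 6 | Days past 405 |
|---|---|---|---|---|
| 16 | 16 (4.0%) | 389 | day 380 | 0 |
| 41 | 41 (10.1%) | 364 | day 405 | 0 |
| 48 | 48 (11.9%) | 357 | day 412 | 7 |
| 62 | 62 (15.3%) | 343 | day 426 | 21 |

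At T = 14 (UCSF) the figures are 14 days (3.5%), 391 days and day 378.

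**4. Infection, rejection and eGFR rows.** Both arms have 405 days. In Group 2 the first T of them are unexposed.

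**5. BK and CMV rows.** If Group 1 is counted from allocation, which the SAP does not state, Group 2 has 343–389 days against 405 (ratio 0.85–0.96).

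**6. Timing rows.** The frame opens at allocation but time runs from the start of treatment. A pre-infusion event in Group 2 would lie inside the frame with a negative time. Group 1 has no defined start of treatment.

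**7. mTOR row.** Protocol 6.1.3 starts everolimus within 2 weeks of the 2-week biopsy. At T = 16 the nominal biopsy is day 30 and conversion falls on days 30–44, so a day-69 start misses 69 − 44 = 25 to 69 − 30 = 39 days after conversion. At T = 62 the nominal biopsy is day 76, 7 days after the frame opens.

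**8. Likely size.** One event in 7 is 1/7 = 14.3 percentage points. The documents give no event rates. Assuming a constant hazard and a 405-day risk p of 10–40%, the chance of an event before infusion is 1 − (1 − p)^(T/405). This runs from 0.4% (p = 10%, T = 16) to 7.5% (p = 40%, T = 62) per participant, or about 0.03 to 0.5 expected events among 7.

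**The case against.** The strongest reply is that 405 is only Group 1's Visit 6 label, not a hard cut. That visit's own window runs to day 419, so a strict cut would truncate Group 1 as well, and SAP 7.1.2 keeps data regardless of timing. This may rescue late Visit 6 results. But SAP 7.1.2 does not say that it overrides the endpoint frames, and it cannot repair where counting starts.

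Counting from allocation is also the usual origin in a randomized comparison, and it gives both arms equal length in the infection, rejection and eGFR rows. That stands: for those rows the fault is attribution, not unequal time.

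A reader might infer that early events count against polyTregs. The documents do not support a direction. Infusion requires that the enrolment criteria are still met (protocol 4.2.1), and these exclude active infection. Uninfused participants are reassigned to Group 1 (SAP 6.2), so an early infection that prevents infusion counts there.

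A reader might also infer that SAP 8.2.1 introduced the unrestricted infection row as an unlogged change. Protocol Table 7 already omits the restriction, so the inconsistency begins in the protocol.

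For BK and CMV the gap is largely nominal. Appendix 2 schedules no BK, CMV or creatinine test in Group 1 between allocation and day 41, so the extra days could add only unscheduled findings.

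Finally, the protocol treats secondary endpoints as descriptive (15.5), and SAP 9.3 lists all adverse events. This limits the consequence but does not settle which events enter the incidence tables.

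**Conclusion.** The point holds for the secondary safety endpoints. Their frame is Group 1's calendar, and it fits Group 2 only at T = 41. Over the permitted range, the infection, rejection and eGFR rows include about 16–62 pre-infusion days (4–15%), with equal length in both arms and unknown direction of bias. The BK and CMV rows lack a Group 1 start. The timing rows use a second origin that is undefined for Group 1, and the mTOR row carries the same day-41 assumption.

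Two wider readings are not supported. One is that the frame always ends before Group 2's final visit. It does so only for infusion after day 41, and only if day 405 is a strict cut. Day 48 should not be taken as the planned infusion day on the strength of Appendix 4, whose table layout is broken; here it is the latest day for someone allocated at the 14-day limit. The other is that the primary safety endpoints share the defect. They carry no 405-day frame, and the SAP synopsis follows safety for the full study.

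The expected numerical effect is small under the assumed risks. The change is still worth making, because the literal text can count infections outside the defined endpoint and can drop a late scheduled BK test.

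**What to change.** In SAP 8.2.1:
- Use one window for the secondary infection, rejection, BK, CMV and eGFR endpoints, for both incidence and timing. It runs from T0 through Visit 6, including the visit window. T0 is infusion in Group 2 and the T0-G1 visit (day 41) in Group 1.
- State T0 for participants reassigned to Group 1, some of whom may be reassigned after day 41.
- Remove the after-infusion condition from the BK and CMV rows, since T0 then supplies the start in both arms.
- Anchor the mTOR row to the actual infusion or conversion date instead of day 69.
- List events between allocation and T0 separately, by allocated and by analysed arm.
- State how SAP 7.1.2 relates to these windows.

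Record the change in SAP section 10, and note there that protocol 3.3.1 and Table 7 differ on the infection endpoint.

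The cost is SAP wording. The dates needed follow from the existing visit schedules. The downside is that Group 1 events before T0 move from the main table to the separate listing. A T0 start does not remove the selection created by re-checking eligibility in Group 2 only, but the listing by both arms makes it visible.
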